12.3 Adverse Event and Serious Adverse Event Reporting

All AEs after signing the ICF through 30 days from the last dose of study treatment will be recorded in the eCRF. All AEs considered related to trial medication will be followed until resolution, return to baseline, or deemed clinically insignificant, even if this occurs post-trial.

SAE reporting begins after the patient has signed the ICF and has received study treatment and for at least 30 days after treatment discontinuation. However, if the investigator learns of any SAE, including a death, at any time after a patient has been discharged from the study, and he/she considers the event reasonably possibly related to the study treatment or study

participation, the investigator must promptly notify Lilly. However, if an SAE occurs after signing the ICF, but prior to receiving study treatment, it needs to be reported **ONLY** if it is considered reasonably possibly related to study procedure.

12.3.1 Reporting to the IRB

Unanticipated problems involving risks to subjects or others will be reported **promptly** to the IRB if they:

- are unexpected;
- are related or possibly related to participation in the research; **and**
- suggest that the research places subjects or others at a greater risk of harm than was previously known or recognized.

If the serious adverse event does not meet all three (3) criteria listed above, the event does not have to be promptly reported to the Indiana University IRB. However, it should be reported at the time of continuing review. **Prompt** reporting of unanticipated problems to the IRB is defined as within 5 days from becoming aware of the event.

12.3.2 Reporting to the FDA

Per CFR 312.32 (c), the investigator-sponsor of the IND must notify the Food and Drug Administration (FDA) and all participating investigators in a written IND safety report of any adverse experience. There are two types of reports to the FDA: 7-day and 15-day reports.

12.3.2.1 15-Day IND Reports

The investigator-sponsor of the IND must notify the Food and Drug Administration (FDA) and all participating investigators in a written IND safety report of any:

- **suspected adverse reaction** that is **both**
- **serious and**
- **unexpected**

Each written notification shall be made as soon as possible, and no later than **15 calendar** days after the investigator-sponsor's initial receipt of the information.

12.3.2.2 7-Day Reports

The investigator-sponsor must notify FDA and all participating investigators in a written IND safety report of any adverse experience:

- **fatal or life-threatening experience** that is **both**
- **associated with use of the drug and**
- **unexpected**

The FDA will be notified as soon as possible but no later than **7 calendar** days after initial receipt of the information.

12.3.2.3 Report Content

Each written notification may be submitted on FDA Form 3500A or in a narrative format and must bear prominent identification of its contents, i.e., “IND Safety Report”. For purposes of this protocol, the **MedWatch Report Form (FDA 3500A mandatory reporting), along with FDA Form 1571, and a cover letter** submitted to the appropriate FDA division, will serve as the written IND safety report. Follow-up information to a safety report should be submitted as soon as the relevant information is available.

Submit

- MedWatch Report Form (FDA 3500A)
- FDA Form 1571
- Cover Letter

The IUSCC Protocol Development Coordinator should be contacted to assist with all FDA submissions and will be provided with a copy of all events that are reported to the FDA. All IND submissions will be maintained in a master file in the Clinical Trials Office of the IU Simon Cancer Center.

12.3.3 Reporting to Lilly

Study site personnel must notify Lilly of any SAE within 24 hours of investigator awareness of the event via the IUSCC SAE form. The form will be submitted with the Lilly study-specific cover letter via Lilly’s Investigator Initiated Research (IIR) portal at <http://LillyInvestigatorResearch.com>. If alerts are issued via telephone, they are to be immediately followed with official notification on study-specific SAE forms. This 24-hour notification requirement refers to the initial SAE information and all follow-up SAE information.

Investigators are not obligated to actively seek AEs or SAEs in patients once they have discontinued and/or completed the study. However, if the investigator learns of any SAE, including a death, at any time after a patient has been discharged from the study, and he/she considers the event reasonably possibly related to the study treatment or study participation, the investigator must promptly notify Lilly.

Pregnancy (during maternal or paternal exposure to study treatment does not meet the definition of an AE but should be reported. However, to fulfill regulatory requirements any pregnancy should be reported following the SAE process to collect data on the outcome for both mother and fetus.

12.4 Suspected Unexpected Serious Adverse Reactions

Suspected unexpected serious adverse reactions (SUSARs) are serious events that are not listed in the IB and that the investigator identifies as related to study treatment or study procedure. United States 21 CFR 312.32 and European Union Clinical Trial Directive 2001/20/EC and the associated detailed guidance or national regulatory requirements in participating countries require the reporting of SUSARs. Lilly has procedures that will be followed for the recording

and expedited reporting of SUSARs that are consistent with global regulations and associated detailed guidance.

12.5 Complaint Handling

Lilly collects product complaints on investigational products and drug delivery systems used in clinical studies in order to ensure the safety of study participants, monitor quality, and to facilitate process and product improvements.

Patients will be instructed to contact the investigator as soon as possible if he or she has a complaint or problem with the investigational product so that the situation can be assessed.

12.6 Treatment of Overdose

Refer to the relevant IB and/or Product Label for LY3214996 and abemaciclib.

13 Data and Safety Monitoring

This study will be conducted in accordance with the IU Simon Cancer Center Institutional DSMP for **High Risk Trials**.

Investigators will conduct continuous review of data and subject safety. **Weekly review meetings** for high risk trials are required and will include the principal investigator, clinical research specialist and/or research nurse (other members per principal investigator's discretion). **Weekly meeting summaries** should include review of data and subject safety by including for each dose level: the number of subjects, significant toxicities as described in the protocol, dose adjustments and responses observed. Study teams should maintain meeting minutes and attendance for submission to the DSMC upon request.

13.1 Data and Safety Monitoring Committee

The IUSCC Data and Safety Monitoring Committee (DSMC) is responsible for oversight of subject safety, regulatory compliance, and data integrity for this trial. The DSMC will review this study semi-annually to review overall trial progress, toxicity, compliance, data integrity, and accrual per the Institutional DSMP.

Furthermore, the DSMC conducts an administrative review of serious adverse events (SAEs), deviations, reportable events, and any other outstanding business. Major issues may require further DSMC review or action.

For any increase in frequency of grade 3 or above adverse events (above the rate reported in the Investigator Brochure or package insert), the principal investigator will notify the DSMC Chair immediately. The notification will include the incidence of study adverse events, grades, and attributions, as well as investigator statements regarding comparison with risks per the IB/ package insert.

At any time during the conduct of the trial, if it is the opinion of the investigators that the risks (or benefits) to the subject warrant early closure of the study, the DSMC Chair and Compliance Officer must be notified within 1 business day via email, and the IRB must be notified within 5 business

days. Alternatively, the DSMC may initiate suspension or early closure of the study based on its review.

13.2 IND Annual Reports

For trials with an IND held locally by the IU principal investigator or university, the IND Annual Report will be prepared and submitted to the Compliance Team. This report will be reviewed by the DSMC at the time of FDA submission.

13.3 Study Auditing and Monitoring

All trials conducted at the IUSCC are subject to auditing and/or monitoring per the Institutional DSMP. Reports will be reviewed by the full DSMC at the time of study review.

13.4 Data Management/ Oncore Reporting Requirements

The DSMC reviews data and study progress directly from Oncore; therefore, timely data entry and status updates are vital. Study data must be entered within Oncore promptly, no later than one week from study visit occurrence. Subject status in Oncore will be updated in real time, as this may affect overall trial enrollment status. Global SAEs and deviations will be reviewed on a monthly basis by the DSMC Chair directly from Oncore.

13.5 Study Accrual Oversight

Accrual data will be entered into the IU Simon Cancer Center OnCore system. The Protocol Progress Committee (PPC) reviews study accrual twice per year, while the PPC coordinator reviews accrual quarterly.

13.6 Oncore Safety Reporting

In addition to protocol- and regulatory-required safety reporting, all serious adverse events (SAEs) will be captured in the Oncore system within 1 business day of notification. Initial SAE reporting will include as much detail as available, with follow-up to provide complete information. Attributions will be assessed to study drugs, procedures, study disease, and other alternate etiology.

13.7 Protocol Deviation Reporting

Protocol deviations will be entered into OnCore within 5 days of discovery and reviewed by the DSMC Chair on a monthly basis. Findings will be reported to the full DSMC at the time of study review. For serious or repetitive protocol deviations, additional action may be required by the DSMC.

14 Statistical Considerations

14.1 Sample Size Determination

The primary end point is overall response rate (ORR), where overall response is defined as the complete or partial response per RECIST criteria. We will use the one stage design for the phase II trial. We will use the one stage design to test the null hypothesis that the true ORR is 5% versus the alternative hypothesis that that the true ORR is 19% using a one-sided test with the designing parameters type-I error=0.05 and type II error=0.2 (power=80%).

A total sample size of 28 evaluable patients will be accrued. The trial is considered a success when the null hypothesis is rejected, which is determined when 4 or more patients have an overall response among the 28 patients. Of note, an evaluable patient is defined as a patient who receives at least one dose of the study drug. Assuming a 20% drop-out rate, it is anticipated that the total accrual would be 35 patients.

We will add additional early stopping rules for the following subgroups of patients with pathogenic alterations in 1) BRAFV600E 2) BRAF nonV600E, RAF1 3) MEK1/2, ERK1/2 and 4) NF1. We will use the Bayesian posterior probability to monitor the response rates for those subgroups. A beta distribution of Beta (0.05,0.05) is assigned as the prior. Then, when every 5 evaluable patients have been enrolled in the specific subgroup under monitoring, we will calculate the posterior probability that the ORR rate for that subgroup is less than 5%. If this posterior probability is greater than 90% during any interim analysis, we will claim that the drug is not promising for this subgroup and will stop any future enrollment for that subgroup of patients. That is, for the 5th, 10th, 15th, 20th, 25th, 30th, and 35th patients in the subgroup, we will determine the enrollment for that subgroup if none of the patients report as tumor response. If the early stopping rule has been triggered, then at the end of the trial we will exclude all the patients in that subgroup from final analysis. We will use a binomial exact test to test the effectiveness of the drug for the remaining patients.

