Pharmacokinetics (PK) ^H			X	X			

A: Medical history to include prior treatments, radiation and surgical history. Diagnosis and staging to include pathology report and Tumor Node Metastasis (TNM) staging 8th edition.
 
B: CTCAE Version [5.0] Adverse Events will be collected from the time informed consent is signed through 30 days after the last dose of study treatment.
 
C: To include albumin, alkaline phosphatase, ALT, AST, bicarbonate, BUN, calcium, chloride, creatinine, glucose, lactate dehydrogenase, magnesium, phosphorus, potassium, sodium, total bilirubin, and total protein.
 
D: All females of childbearing potential must have a negative blood or urine pregnancy test within 14 days prior to enrollment and prior to treatment on day 1
 
E: CT or MRI scans of chest and abdomen will be done at baseline to assess the response per RECIST v1.1 criteria. CTs or MRIs of the abdomen with IV contrast are encouraged but will be done at the investigator's discretion. Disease assessments should be completed every odd cycle (i.e. cycle 3, cycle 5, etc.).
 
F: Antiemetic prophylaxis will be required in cycle 1 in an effort to improve patient safety and reduce the incidence of nausea and vomiting. Refer to Section 8.6.1.3 for details.
 
G: Biopsy at screening is mandatory if deemed safe by the treating physician and should be completed following determination of eligibility, ≤14 (+/- 7) days before start of treatment. Patients unable to undergo the screening biopsy may donate archived tissue if available. See Section 10.5.2 for details. Biopsy at time of progression is not mandatory.
 
H: Plasma samples for pharmacokinetics will be collected on cycle 1 day 15 and cycle 2 day 1 prior to dosing of abemaciclib and LY3214996. Please refer to Section 10.3.
 
I: Vital signs to be performed per standard of care and should include heart rate, blood pressure, respiratory and oxygen saturation
 
J: To include WBC, ANC, platelets, and Hgb
							

3 Introduction

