14.2 Populations for Analyses

The following populations will be defined for this study:

Safety population: will include all enrolled patients who received any quantity of study treatment, regardless of their eligibility for the study.

Efficacy Population: will include all enrolled patients who received any quantity of study treatment, regardless of their eligibility for the study.

Biomarker population: will include the subset of patients from the safety population from whom a valid assay results have been obtained.

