14.3.2 Efficacy Analyses

14.3.2.1 Endpoints

Overall response rate is defined as the number of patients who achieve a best overall response of complete response (CR) or partial response (PR) divided by the total number of patients treated (efficacy population).

Progression-free survival (PFS) is defined as the time from the date of start of treatment to the first date of the observed clinical or radiologically documented PD or death due to any cause, whichever occurs first. For patients who are not known to have died or progressed as of the data-inclusion cut-off date, PFS time will be censored at the date of the last objective progression-free disease assessment prior to the date of any subsequent systematic anticancer therapy.

The duration of overall response is measured from the time measurement criteria are met for CR or PR (whichever is first recorded) until the first date that recurrent or progressive disease is objectively documented (taking as reference for progressive disease the smallest measurements recorded since the treatment started).

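### Dropping futility-closed subgroups from the final test selects patients on the primary outcome, contradicts the all-treated ORR and the 4-of-28 rule, and leaves the 5% type I error unprotected

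*Combined protocol and SAP*

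**What the plan says.** Section 14.1 sets a one-stage, one-sided test of ORR 5% against 19% with 28 evaluable patients (at least one dose). Success is declared "when 4 or more patients have an overall response among the 28 patients".

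The same section adds futility monitoring in four molecular subgroups with a Beta(0.05, 0.05) prior. A look takes place "when every 5 evaluable patients have been enrolled in the specific subgroup under monitoring", and a subgroup closes if the posterior probability of an ORR below 5% exceeds 90%. The plan's own gloss is that "we will determine the enrollment for that subgroup if none of the patients report as tumor response". If a subgroup closes, "at the end of the trial we will exclude all the patients in that subgroup from final analysis", and "We will use a binomial exact test to test the effectiveness of the drug for the remaining patients".

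Elsewhere the primary population is everyone treated. Section 14.2 reads "Efficacy Population: will include all enrolled patients who received any quantity of study treatment, regardless of their eligibility for the study", and Section 14.3.2.1 has responders "divided by the total number of patients treated (efficacy population". Section 14.3.2.2.1, the primary analysis, repeats the one-stage test and does not mention the exclusion.

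On scan timing, Table 2.1 footnote E says "Disease assessments should be completed every odd cycle (i.e. cycle 3, cycle 5, etc".

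**The concern.** Two problems follow.

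First, the primary population and the success threshold are each defined in two ways. Suppose three subgroups close at 0/5 and the fourth has 3/13. The test on the remaining patients succeeds, because P(X≥3 | n=13, 5%) = 0.0245. The stated rule fails, because 3 of 28 is below 4 (P(X≥3 | n=28, 5%) = 0.163).

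Second, removal depends on the outcome being tested. When responses are known at each look, only non-responders are dropped: the numerator stays, the denominator shrinks and the critical value can fall with it. An unadjusted binomial test on the survivors does not have its nominal level, and their ORR is on average too high. If scans lag behind the looks, the error reverses: a closed subgroup may contain patients who respond later, and they are discarded too.

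This is the trial's single primary test, and no operating characteristics are given for the combined procedure.

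**Working it through.** **Inputs.** From Section 14.1: p0 = 5%, p1 = 19%, one-sided 0.05, n = 28, success at ≥4, prior Beta(0.05, 0.05), looks at every 5 patients per subgroup, closure above 0.90, four subgroups, accrual 35. Subgroup mix, refilling and scan lag are assumptions, because the documents state none.

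**The plan's own figures.** P(X≥4 | 28, 0.05) = 0.0491. P(X≥4 | 28, 0.19) = 0.8065. 28/(1 − 0.2) = 35. All reproduce.

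**When a subgroup closes.** The posterior after x responses in n is Beta(0.05 + x, 0.05 + n − x). At 0/5, P(ORR<5%) = 0.945, so it closes. With one response the value is 0.170 at n=5, 0.348 at n=10 and at most 0.812 at n=35. So only zero responses closes a subgroup.

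**A case worked by hand: fixed 7/7/7/7, no refill, true ORR 5%.** A subgroup closes with probability 0.95^5 = 0.7738 and stays open with 0.2262. An open subgroup has exactly one response with joint probability 0.1838, so P(≥2 responses | open) = 1 − 0.1838/0.2262 = 0.1876. Every open subgroup has at least one response. With one, two or three open, the critical value is one more than the number open, so the test rejects if any open subgroup has two or more responses.

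| Open subgroups | n left | Critical value | P(this many open) | P(reject, given this many open) | Product |
|---|---|---|---|---|---|
| 0 | 0 | none defined | 0.3585 | counted as 0 | 0 |
| 1 | 7 | 2 | 0.4192 | 0.1876 | 0.0787 |
| 2 | 14 | 3 | 0.1838 | 1 − 0.8124² = 0.340 | 0.0625 |
| 3 | 21 | 4 | 0.0358 | 1 − 0.8124³ = 0.464 | 0.0166 |
| 4 | 28 | 4 | 0.0026 | 1 | 0.0026 |

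The products sum to **0.160**.

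**Other accrual assumptions.** True ORR is 5% in all subgroups, responses are known at each look, and the critical value follows the remaining n. Simulations use 200,000 trials per scenario and five mixes from 25/25/25/25 to 80/10/5/5.

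| Scenario | Type I error |
|---|---|
| 28 treated, open subgroups refill | 6.7–7.8% |
| Refill until 28 remain, at most 35 treated | 7.5–9.2% |
| Refill until 28 remain, no cap | 10.3–13.5% |
| Fixed splits of 28, no refill (exact, all 169 with four non-empty subgroups) | 3.2–16.0%, median 5.9% |
| 28 treated, all treated patients analysed at ≥4 | 4.8–5.0% (bounded by 4.91%; the excess is simulation error) |

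**Scan lag.** Looks are triggered by enrolment, while the first on-treatment scan is at cycle 3, about 56 days in. The synopsis expects 35 patients in 12 months, so about 35 × 56/365 = 5.4 patients enrol in that window over all subgroups. Taking the last 1 to 4 patients of the subgroup as unassessed at each look (28 treated):

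| Unassessed at each look | Type I error | Power at 19%, with exclusion | Power at 19%, all treated analysed |
|---|---|---|---|
| 1 | 5.8–6.9% | 79–80% | 80% |
| 2 | 4.8–5.6% | 73–75% | 78% |
| 3 | 3.5–4.2% | 62–65% | 74% |
| 4 | 1.9–2.3% | 42–44% | 66% |

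**Estimated ORR.** With random accrual and no lag, the mean ORR among retained patients, when anyone remains, is 9–13% at a true 5% and 22–25% at a true 19%. About 36% of these null trials retain nobody, and the plan defines no test for that outcome. Counting them as 0, the mean at a true 5% is 5.5–8.0%.

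**The case against.** The strongest reply is that inflation depends on one reading. If the count of 4 is kept with 28 treated in total and no lag, type I error stays at 4.8–5.0% even after exclusion, because only non-responders are dropped. That is correct, but it holds only for a total of 28 treated. If enrolment refills until 28 remain, capped at 35 treated, the ≥4 rule itself gives 7.5–9.2%. An exact test on the remaining patients also naturally implies a critical value for that smaller n.

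The extremes are also open to challenge. The 16% needs a fixed equal split with no refilling, although the plan intends to accrue 28. The uncapped figures exceed the planned 35. The 2% comes from a four-patient scan lag. Equal weighting of the 169 splits has no basis in the plan. These points stand, so the 7–9% range is the more representative figure when responses are known at each look.

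It can also be said that Section 14.1 is a prespecified exception to the general definitions. Writing it down in advance does not make an unadjusted test valid after outcome-based selection, and the primary analysis section does not refer to it.

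Two limits are accepted. The upward bias is an average, not present in every trial. Retaining response-free subgroups that never reached five patients adds non-responders, so it is an inconsistency and not a source of inflation. The documents do not say that looks precede scans; they leave it open.

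**Conclusion.** The concern holds and must be fixed. The contradiction over population, denominator and threshold needs no assumptions. That only zero-response subgroups can close follows directly from the stated prior and cut-off.

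The size is conditional. If the critical value follows the remaining n and responses are known at each look, type I error is 6.7–9.2% in the refilling scenarios that keep to 28 or at most 35 treated. The wider range of about 2–16% reflects accrual and scan-timing rules that the plan leaves unstated. The 5% level is therefore not guaranteed; it is not always exceeded. With substantial lag the test becomes conservative and the loss is in power, down to 42–44% at a four-patient lag.

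**What to change.** Delete the exclusion sentence in Section 14.1 and make the exact test apply to all treated patients, in line with Sections 14.2 and 14.3.2.1. Use the futility rule only to close enrolment to a subgroup. Then:

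- Declare success at ≥4 of 28, or at the exact critical value for the actual number treated. For 29 to 35 treated that value is 5, with type I error 1.4–2.9%. Reusing 4 would give 5.5–9.6%.
- Report the ORR of every subgroup, open or closed, with an exact confidence interval.
- State whether closed places are refilled, and whether a look waits for the scans of the patients it counts.

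If the sponsor prefers to keep the exclusion, derive the critical values by simulation at ORR 5% in every subgroup under stated mix, refill and lag assumptions, define the result when no patients remain, and restate the power.

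The change is a few sentences, but it has costs. The pooled ORR will be lower, because non-responders in closed subgroups stay in the denominator. Power of about 81% needs open subgroups to refill to 28 treated; with a fixed 7/7/7/7 split and no refill it is 70%. Overshooting 28 also matters: at the critical value of 5, power is 66.9% with 29 treated and 82.1% with 35, so the target number treated should be fixed.
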